2.0 OBJECTIVES

2.1 Primary objectives:

Assess 5-year biochemical failure free rate (BFFR) associated with the combined hypofractionated dose regimen and ADT. The BFFR is defined as a binary indicator whether

PSA has increased by 2 ng/ml or more above the nadir PSA any time before the end of 5 years.

2.2 Secondary objectives:

- 1) Assess the incidence of grade 3 or greater late GU and GI toxicity and self-reported quality of life data.
- 2) Assess clinical and pathologic control rates associated with the combined hypofractionated dose regimen and ADT using Kaplan-Meier estimates.
- 3) Collect dose/volume and imaging data to allow normal tissue complication probability modeling and targeting assessment for patients treated with hypofractionated radiation therapy.
- 4) Collect whole blood to perform correlative studies for serum cytokine profiling and future biomarker studies.

3.0 PATIENT SELECTION: The target population will be patients with a diagnosis of adenocarcinoma of the prostate who are seen in consultation in the Department of Radiation Oncology (approximately >1000 patients per year).

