Overall survival (OS), measured from date of enrollment to date of death using Kaplan-Meier estimates. Every effort will be made to document the cause of death.

8.2.3 Collect dose/volume and imaging data to allow normal tissue complication probability modeling and targeting assessment for patients treated with hypofractionated radiation therapy and ADT.

Voxel level dose distribution, normal tissue complication, and tumor control will be collected. All images will be co-registered and normalized. Functional principal component analysis will be used to develop dose response and tumor control models.

8.2.4 To explore the changes in serum levels of inflammatory and angiogenic cytokines as biomarkers of treatment response, we will use Bioplex 200 technology to batch analyze a 27 cytokine panel in parallel at baseline and after 3 and 24 months of completing treatment. The blood collected in one 8 ml serum separation tube (BD vacutainer, lavender-top) will be allowed to stand 45-60 minutes and processed within one hour. The tube will be centrifuged at 1200g for 10 min in a swing out rotor (approximately 2500rpm). The serum will be transferred into a clean empty 15ml tube using Pasteur pipette. The serum will be aliquoted into 1.05 ml volume in each cryopreservation vial and stored in -80°C or -20°C freezer. We will process the samples as described previously by our Co-I [name]. Briefly, The Bioplex 200 (Bio-Rad, Hercules, CA) platform will be used to determine the absolute concentration (in pg/ml) of 27 target proteins in banked sera samples. A multiplexed bead-based immunoassay is performed in duplicate for each serum sample following the manufacturer's protocols and using the supplied cytokine standards. The concentration of each cytokine will be determined using a 5-parameter log curve fit using the supplied software. The Human 27-plex panel includes validated assays for IL-1b, IL-1ra, IL-2, IL-4, IL-5, IL-6, IL-7, IL-8, IL-9, IL-10, IL-12(p70), IL-13, IL-15, IL-17, eotaxin, basic FGF, G-CSF, GM-CSF, IFNg, IP-10, MCP-1, MIP1a, MIP1b, PDGF-BB, vascular endothelial growth factor (VEGF), and TNFa. This data will be correlated with primary and other secondary objectives.

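### Section 8.2.4 describes the cytokine blood tube in a way that conflicts with its own serum procedure, and leaves the storage temperature open

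*Combined protocol and SAP*

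**What the plan says.** The cytokine work is item 4 of the secondary objectives in section 2.2: "Collect whole blood to perform correlative studies for serum cytokine profiling and future biomarker studies". Section 8.2.4 gives the aim as "To explore the changes in serum levels of inflammatory and angiogenic cytokines as biomarkers of treatment response" and sets the collection rule: "one 8 ml serum separation tube (BD vacutainer, lavender-top) will be allowed to stand 45-60 minutes and processed within one hour". After centrifugation, "The serum will be transferred into a clean empty 15ml tube using Pasteur pipette". Storage follows: "The serum will be aliquoted into 1.05 ml volume in each cryopreservation vial and stored in -80°C or -20°C freezer". Concentrations are then measured in pg/ml in the banked sera and related to the primary and other secondary objectives.

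Section 6.1 makes the draws optional, at baseline and at 3 and 24 months after treatment, and bars men who began ADT before consenting to them. Section 9.0 lists several sites, and section 16.0 makes participating sites responsible for following the protocol as written.

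For collection, section 8.2.4 names no additive, catalogue number or laboratory manual. It does not ask for the tube or freezer to be recorded, sets no limit on storage time, and states no adjustment for site, tube or storage.

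**The concern.** There are two separate gaps.

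**Tube.** A collection rule should lead every site to the same specimen. Here the tube's name and its colour point to different specimens under the usual colour code. EDTA blood does not clot on standing, and spinning it gives plasma. A site that picks the tube by colour would bank a different matrix from a site that picks it by name, and the matrix cannot be changed once the sample is frozen.

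**Storage.** Two temperatures are allowed, with nothing to keep a man's samples together on one of them. Storage time may also differ systematically by visit. The trial has one regimen and no control arm, so a drift that follows visit would look the same as a change after treatment.

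At stake is the interpretation of cytokine change, and of its correlation with the other outcomes.

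**Working it through.** The plan gives no figure to reproduce here. The check is a comparison of wording, plus one sum for storage time.

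**Step 1: which matrix does the text call for?**

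- Section 2.2, item 4: serum profiling.
- Section 8.2.4, aim: serum levels.
- Section 8.2.4, tube name: serum separation tube.
- Section 8.2.4, tube colour: lavender.
- Section 8.2.4, transfer, aliquoting and assay: serum, then banked sera.

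The colour is the only element that points away from serum. Plasma and anticoagulant are not mentioned anywhere. The conflict depends on the colour convention, which is general laboratory knowledge and is taken here as an assumption.

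**Step 2: how much longer does a baseline sample wait?** This step assumes that a man's samples are all assayed on one date. If the assay date is A, the baseline date is b and the 24-month draw is at b + g, the difference in storage time is (A − b) − (A − b − g) = g. The inputs to g are:

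- The baseline draw precedes ADT. This is inferred from the section 6.1 bar on earlier ADT and the pre-treatment column of the section 7.0 calendar.
- ADT start to radiation start is at least 1 month (section 5.5; section 7.0, note 13).
- Radiation lasts 2 weeks, about 0.5 month (section 7.0, note 14).
- The end of radiation to the last draw is 24 months (section 7.0), with a window of ±30 days, about 1 month (note 16).

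g = 1 + 0.5 + 24 = 25.5 months at the nominal visit, and 25.5 − 1 = 24.5 months at the early edge of the window. Both are minimum values, because the ADT lead-in may exceed 1 month and the draw may precede ADT by some interval.

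**Step 3: what does that do to a change?** Write L(s) for the log-scale loss after storage time s. Then

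observed log change = true log change + L(s at baseline) − L(s at 24 months), with s at baseline = s at 24 months + g.

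If loss grows with time, the added term has the same sign in every man. It is present even if one freezer temperature is used throughout. A change of freezer or tube between visits would add a further term.

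**Step 4: can it be sized?** No. The documents give no stability data, no serum-to-plasma ratio, no cytokine standard deviations, no number of samples, and no split by tube or freezer.

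**The case against.** The strongest reply is that one word is wrong. Every other cue says serum, so the colour is most likely a labelling slip, and a laboratory using one tube throughout would have no matrix shift within a man. This largely stands. A reader might infer that sites did bank different matrices, but the text only leaves that open. What remains is that the rule, followed as written, can yield the wrong specimen.

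Section 8.2.4 also refers to an earlier description of sample processing by a co-investigator. That source might settle the tube and the freezer, but it is not part of the documents.

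On storage, the single-batch reading is not certain. The sentence about batching could mean one run per time point, in which case the gap in step 2 disappears. The reference to banked sera makes a common run the likelier reading, but does not prove it.

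Four stronger readings should be set aside:

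- The two temperatures do not contradict each other. They are an uncontrolled choice, and temperature does not alter the matrix.
- The stand time and the one-hour limit collide only at 60 minutes, and only if both clocks start at the draw.
- The list under the 27-plex panel names 26 analytes, but no analytic consequence is shown.
- Any percentage put on the artefact would be hypothetical.

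**Conclusion.** The point holds in limited form. The tube description in section 8.2.4 conflicts with the serum procedure, given the usual colour convention. The storage temperature is not standardised. If visits are assayed together, baseline samples are stored at least about 24.5 to 25.5 months longer than 24-month samples, so storage loss could be confounded with visit. That an artefact exists, and how large it would be, cannot be established from the documents.

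The reach is narrow: optional samples serving an exploratory objective for which no change endpoint or test is defined. The estimate of the 5-year biochemical failure-free rate, the sample size of 110 and the toxicity stopping boundary do not depend on it. The point still merits correction, because cytokine profiling is a listed secondary objective, the blood is also meant for future biomarker studies, and the results are to be correlated with the main outcomes.

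**What to change.** **In the text of section 8.2.4:**

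- Delete the lavender-top descriptor and name one serum tube for all sites and visits. If plasma is what was intended, correct the matrix wording throughout instead.
- Require one storage temperature for all aliquots. Since -80°C is already allowed, deleting the -20°C option is enough.

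**For samples already banked:**

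- Establish and record tube type, freezer temperature and storage time for each sample.
- Restrict within-man change analyses to pairs of the same matrix and storage temperature.
- Report storage time by visit, or adjust for it.

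The second group probably matters more. The document carries a December 2021 date, while section 9.0 projected accrual to close in August 2015, so most draws have probably been taken. Actual dates are not given.

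The cost is a one-paragraph amendment and a records check. Mismatched pairs leave the change analysis. Adjustment for storage time will be only partial: under a common run the baseline-to-24-month gap is nearly the same for every man, so the model would have to rely on differences in storage time between men.

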5.5 Androgen Deprivation Therapy (ADT)

Androgen deprivation therapy, also known as hormonal ablation, is designed to inhibit the effects of testosterone on prostate cancer cells. This will be accomplished by medications designed to block testosterone production in the hypothalamus (goserelin/leuprolide/triptorelin) and medications designed to block testosterone receptors at the cell surface (bicalutamide). Each of these drugs is approved by the FDA for the treatment of prostate cancer. Goserelin, leuprolide, or triptorelin will be used for four months (≥ 1 month prior to radiation therapy), with at least two weeks of bicalutamide prior to start of RT. Bicalutamide may be continued through the duration of radiation at the physician's discretion. Doses and drug information may be found at the websites below:

- Goserelin (Zoladex®) – http://www1astrazeneca-us.com/pi/zoladex3_6.pdf
- Leuprolide (Lupron®) - http://pitapabbott.com/lupron3month22_5mg.pdf
- Triptorelin (Trelstar®) -
http://pi.actavis.com/data_stream.asp?product_group=1684&p=pi&language=E
- Bicalutamide (Casodex ®) - <http://www1astrazeneca-us.com/pi/casodex.pdf>

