6.0 PATIENT ASSESSMENTS

6.1 Study Parameters

- H&P – at initial consult and following treatment protocol
- PSA – At baseline, 3 and 6 months after treatment, then every 6 months until 3 years, and then annually until year 5
- Testosterone – At baseline, 3 and 6 months after treatment, then every 6 months until 3 years, and then annually until year 5
- Bone Scan - at baseline*
- Pelvic CT or other lymph node assessment - at baseline*
- Symptom assessment (IPSS, SHIM, modified EPIC sheet, as per Appendix I) – At baseline, 3 and 6 months after treatment, then every 6 months until 3 years, and then annually until year 5
- Serum ALT, AST and AP at baseline and one month following initiation of ADT.
- Optional Blood draw collected at baseline and at 3 and 24 months following treatment completion. Patients who have initiated ADT prior to consent for optional blood samples will be ineligible to give extra blood samples.
- Seed placement of at least 3 gold seeds at least 1 week prior to first CT simulation if additional image guidance is not being used
- CT simulation will occur prior to radiation treatment as standard of care and then again during radiation any time after fraction 3 as a QA procedure for monitoring prostate rotation in relation to seed placement. However, second CT simulation after fraction 3 is only necessary if patient had fiducial placement.

* CT/MRI and Bone scan optional except for the patients who are:

1. Gleason 4+3
2. >50% cores positive
3. >1 intermediate risk factor (GS 7, PSA ≥ 10 and T2b-T2c).

Safety run-in phase

A phase I trial of SBRT in prostate cancer (n=45) composed of 60% intermediate-risk, localized patients where 22% of men were treated with androgen deprivation has been recently reported (ref. 7). This trial used considerably higher SBRT doses than our current trial (9-10 Gy x5 versus 7.25 Gy x5) and still reported no Grade 3 or 4 GI or GU acute toxicities (<90 days). Therefore, we believe our more modest SBRT fractionation scheme of 7.25 Gy x5 is likely safe in combination with androgen deprivation. To ensure that this combination is safe, the first six patients will be treated and analyzed for toxicity for 3

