7.0 STUDY CALENDAR

	Pre-treatment	Radiation ¹⁴	Follow-Up ¹⁶ (in time post radiation treatment)										
			1 mo	2 mo	3 mo	6 mo	12 mo	18 mo	24 mo	30 mo	36 mo	Year 4	Year 5
Initial Consult	X												
Consent	X												
History and Physical	X				X	X	X	X	X	X	X	X	X
Digital Rectal Exam¹⁵	X				X	X	X	X	X	X	X	X	X
Biopsy¹²													
Histological Diagnosis¹	X												
MRI *	X ³												
Pelvic CT scan *	X ³												
Bone scan *	X ⁴												
Cardiovascular risk assessment	X ⁵												
Quality of Life measures⁶	X				X	X	X	X	X	X	X	X	X
Toxicity assessment⁹	X	X			X	X	X	X	X	X	X	X	X
Biomarker blood draw (optional)	X				X				X				
Serum ALT, AST, and AP¹⁰	X												
Seed placement⁷	X												
CT Simulation¹⁷	X	X											
PSA¹¹	X ²				X	X	X	X	X	X	X	X	X
Testosterone	X				X	X	X	X	X	X	X	X	X
LHRH agonist¹³	X	X	X	X									
Bicalutamide⁸	X	X	X	X									

¹Histological diagnosis and Gleason score provided on the pathology report. All patients, per institutional policy, will have pathology reviewed at Johns Hopkins

²PSA within 4 months prior to registration

³CT scan or MRI of the pelvis within 6 months prior to registration. Lymph nodes evaluated negative by imaging methods will be classified as NX. Only nodes evaluated negative by surgical sampling will be classified as N0.

⁴Bone scan within 2 months prior to registration

⁵Cardiovascular risk assessment if the patient is determined to be "high risk" for vascular event – prior MI or stroke within 5 years

⁶IPSS (less than 16 or patient is excluded from trial participation), SHIM, and modified EPIC bowel questionnaires

⁷At least 1 week prior to simulation, patients will undergo transrectal or transperineal inserting of at least 3 gold seeds to improve accuracy in daily prostate alignment and decrease residual positioning errors. However, if additional image guidance is being used, fiducials will be optional.

⁸At least two weeks of bicalutamide at the initiation of hormone therapy and may be continued through the duration of radiation at the physician's discretion.

⁹Patients will be seen one time by the radiation oncologist during treatment

¹⁰Serum ALT, AST and AP collected before the initiation of ADT and one month (+/- 14 days) following initiation of ADT

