8.0 DATA ANALYSIS AND SPECIAL CONSIDERATIONS

8.1 Primary Analysis:

The primary objective is to estimate the 5-year biochemical failure free rate (BFFR) associated with the combined hypofractionated dose regimen and ADT. The BFFR is defined as a binary indicator whether PSA has increased by 2 ng/ml or more above the nadir PSA any time before the end of 5 years. The primary analysis will be performed by first obtaining the Kaplan-Meier (K-M) estimate of the biochemical failure free survival, and then estimating the 5-year biochemical failure free rate (BFFR) from this K-M curve together with 95% confidence interval. Greenwood formula will be used to calculate the variance of K-M estimate.

8.2 Secondary objectives:

8.2.1. Assess the incidence of grade 3 or greater late GU and GI toxicity and self-reported quality of life data.

Kaplan-Meier estimate of the incidence of grade 3 or greater late GU and GI toxicity will be constructed together with 95% confidence interval. Patient reported quality of life will be summarized using means and standard deviation for continuous measures, the contingency tables for categorical measures.

8.2.2 Assess clinical and pathologic control rates associated with the combined hypofractionated dose regimen and ADT.

Assessments will be performed 3 and 6 months after treatment and then every 6 months until 3 years, then annually until year 5. These rates will be estimated from Kaplan-Meier curves together with 95% confidence intervals.

Disease-Free Survival, measured from the date of enrollment to the date of documented progression or date of death using Kaplan-Meier estimates. Progression will be documented by PSA, bone scan, or biopsies.

Time to Local Progression (TLP) will be measured from the date of enrollment to the date of documented local progression using Kaplan-Meier estimates. Patients with new palpable abnormality on digital rectal examination or PSA failure at any point in time will also be offered biopsy to distinguish between local and distant failures. Patients who do not undergo biopsy will be censored at the last point of time they were considered locally controlled by digital rectal examination and PSA and considered not evaluable for further assessment.

Time to Distant Failure (TDF) will be measured from the date of enrollment to the date of documented metastatic disease. Patients who have negative biopsy following PSA failure or palpable abnormality will be considered to have only distant failure.

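### The 24-month cytokine values are to be related to endpoints that include events before month 24; section 8.2.4 needs a landmark or time-dependent rule (minor)

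*Combined protocol and SAP*

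**What the plan says.** Section 8.2.4 states an exploratory aim: "To explore the changes in serum levels of inflammatory and angiogenic cytokines as biomarkers of treatment response". It assays a "27 cytokine panel in parallel at baseline and after 3 and 24 months of completing treatment", and after the laboratory method gives the whole association analysis in one sentence: "This data will be correlated with primary and other secondary objectives". No test, risk set, start of the time axis or handling of samples taken after an event is given.

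Section 8.1 defines the primary endpoint by whether "PSA has increased by 2 ng/ml or more above the nadir PSA any time before the end of 5 years". Kaplan-Meier estimation with Greenwood variance is specified there for that rate, not for the cytokines. Section 8.2.2 measures disease-free survival, local progression, distant failure and overall survival from enrollment.

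Section 6.1 makes the sampling voluntary: "Optional Blood draw collected at baseline and at 3 and 24 months following treatment completion". Men who began ADT before consenting to the samples cannot give them. PSA failure is not among the withdrawal reasons in section 14.0, so a man who fails at month 12 can still give a 24-month sample.

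**The concern.** A marker measured at month 24 can predict only what happens after month 24. Read literally, section 8.2.4 relates it to a 5-year indicator that also counts earlier failures, and to time-to-event endpoints that start at enrollment. Two problems follow.

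- **Order of events.** For a man who failed before month 24, the sample may show the effect of recurrence or its treatment. The outcome then influences the marker.
- **Selection.** A 24-month value exists only for men still alive and attending at that time. Counting their survival from enrollment credits them with two years in which they could not have died and still have a value.

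At stake is the interpretation of any cytokine reported as a biomarker of treatment response. One that merely follows failure could be reported as if it had foretold it.

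**Working it through.** **1. The plan's own figure.** Section 8.2.4 states none. The nearest is the precision statement in section 8.3: with 85% and 100 completers, the 95% CI width is 2 × 1.96 × √(0.85 × 0.15 / 100) = 0.13997, which agrees with the stated limit of 0.14. So 85% at 5 years is the planning value to use.

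**2. How many failures precede month 24?** The documents give no hazard shape, so assume a Weibull form: S(t) = exp[−H (t/60)^k], with H = −ln 0.85 = 0.1625 and t in months.

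For a constant hazard (k = 1), failures by month 24 are 1 − 0.85^(24/60) = 1 − 0.937 = 6.3 per 100 men. That leaves 15 − 6.3 = 8.7 after month 24.

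| k | Failures by month 3 | By month 24 | After month 24, to year 5 |
|---|---|---|---|
| 0.7 | 2.0 | 8.2 | 6.8 |
| 1 | 0.8 | 6.3 | 8.7 |
| 1.5 | 0.2 | 4.0 | 11.0 |
| 2 | 0.04 | 2.6 | 12.4 |
| 2.5 | 0.01 | 1.6 | 13.4 |

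All figures are per 100 men. Early failures are 11% to 55% of the total. At month 3 the problem is negligible, at most about 2 men.

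Section 8.3 expects 85% or higher. At 93%, the 5-year PSA control that section 1.0 quotes for a brachytherapy series, a constant hazard gives 2.9 early and 4.1 later failures.

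**3. What this does to a non-predictive marker.** Assume 110 men, all sampled, with 16 failures (0.15 × 110 = 16.5). The cytokine has SD 1 and no prognostic value, and is shifted by s SD in the E men who failed before the draw. All failures are compared with all non-failures by a two-sided 5% t-test. The expected spurious difference is sE/16, and its standard error is about √(1/16 + 1/94) = 0.270.

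For E = 5 and s = 1, the difference is 0.3125, or 1.16 standard errors. The rejection rate is about P(Z > 1.96 − 1.16) ≈ 21%. Simulation (40,000 runs) gives:

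| Early failures | Shift 0.5 SD | Shift 1 SD |
|---|---|---|
| 3 of 16 | 6.4% | 10.0% |
| 5 of 16 | 9.0% | 20.1% |
| 6 of 16 | 10.2% | 26.7% |

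With no shift the rate is 5%. Restricting the comparison to men event-free at month 24 gives 4.8% to 5.1% throughout.

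**4. Half the men sampled.** With 55 men, 8 failures, 2 or 3 of them early, and a 1 SD shift, the rate is about 9% to 16%. Optional sampling reduces the inflation but does not remove it.

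**5. Missing 24-month samples.** At the planned dropout of 1% to 2% a year, about 110 × 0.01 × 2 = 2 to 110 × 0.02 × 2 = 4 men leave by month 24. Deaths are not projected in the documents.

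**The case against.** The strongest reply is that the plan names no method. A month-24 landmark fits its wording as well as a comparison with all failures does, so bias has not been shown. That stands as far as it goes: the inflation needs both the all-failures comparison and a real shift after failure. But the literal instruction covers all the cytokine data and the whole 5-year endpoint, and nothing in the text rules out the faulty analysis.

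It can also be said that a cytokine altered by failure is truly associated with response. That too stands: the result is spurious only if read as predictive. The landmark keeps the two readings apart.

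The magnitude rests on assumptions. The shift size is not in the documents, and 16 failures is the upper end of what section 8.3 expects. Multiplying a rate by 27 to get a count of false findings would require all 27 cytokines to shift by the same amount, which nothing supports. Late toxicity is left out of the argument because section 8.2.1 does not state when its clock starts.

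A reader might also infer that the baseline-to-3-month change is biased because it mixes ADT with radiation. The documents do not support that. The regimen under study is the combination, so a change reflecting both is the response to the study treatment; it only limits attribution to radiation alone, which the plan does not claim. Adjusting for same-visit testosterone would condition on something ADT itself changes. An extra tube at the liver-function draw, scheduled "one month (+/- 14 days) following initiation of ADT", would be a new procedure that this point does not call for.

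**Conclusion.** The concern holds for the 24-month values. The plan relates them to endpoints that count earlier events and gives no rule for samples taken after an event. Under the stated assumptions the false-positive rate per cytokine is about 6% to 27% with all 110 men sampled, and about 9% to 16% with half sampled and a 1 SD shift. It is 5% if failure leaves the marker unchanged. The hazard shape, the shift and the number of men giving samples are all assumed. It would go too far to say that the planned biomarkers are biased as a matter of fact, or that the 3-month comparison is materially affected.

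Severity is minor. The analysis is exploratory, sampling is optional, and neither the BFFR estimate nor the sample size depends on it.

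**What to change.** Add to section 8.2.4:

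- Relate the 24-month values, and changes to month 24, only to events after the draw date. Include only men who at that date are event-free and have had no further prostate cancer therapy. Start the clock at the actual draw, since the study calendar allows 30 days either side, and treat a failure documented on the draw date as having occurred before it. A time-dependent covariate model is an acceptable alternative.
- Use the baseline values for whole-period 5-year BFFR.
- Apply the same rule at 3 months for consistency. It will change little there.

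This needs wording only and uses data already scheduled. The cost is that early failures leave the 24-month comparison: about 9 events rather than 15 per 100 men under a constant hazard, so less power. The rule returns each test to its nominal level, but it does not address the testing of 27 cytokines.
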